## SECTION 2. Assessment and Evaluation of the Risks

For details, refer to the UK IRB's [Policy on Children in Research](#).

A. Provide justification for the participation of children as research subjects in your study.

The purpose of the study is to assess the effects of an adapted evidence-based parenting intervention on parent behaviors, child behaviors, child adherence to wearing their hearing equipment, and child speech/language outcomes. For all four outcomes, participation of the children is needed in assessment of outcomes, including videotaped tasks, parent-report measures, and measures administered directly to children. Children's direct participation in the parenting intervention is not necessary.

B. Has this research been conducted in adults? ☒ Yes ☐ No

If yes, is there any indication that the proposed research would benefit, or at least not be harmful to children?

There are 40 years of research evidence demonstrating the benefits of evidence-based parenting interventions to children and families.

C. Indicate how many children you propose to enroll in the study:

**Note:** Whenever possible, involve the fewest number of children necessary to obtain statistically significant data which will contribute to a meaningful analysis relative to the purpose of the study.

Justify this number:

Two children have already participated in Aim 3, the piloting of trial procedures. We plan to enroll 125 parent-child dyads (125 parents, 125 children; 72 dyads randomized to the intervention and 53 dyads randomized to the control condition) in the effectiveness trial, Aim 4. This number was determined by our biostatistician based on the individually-randomized trial design,  $\alpha=.05$ , the potential of clustering at the interventionist level, and the need to detect a medium-sized effect on the primary outcome (parenting behaviors).

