minutes); the 24-item PARYC (10 minutes); the 19-item PSCS (5 minutes); the 21-item BDI-II (5 minutes); the 25-item PMI (10 minutes); and the MacArthur Bates Words & Sentences form (20 minutes) or the MacArthur Bates Words & Gestures form (20 minutes) for children who do not yet produce 10 or more spoken words. Parents will also participate in a structured interview with the data collector to complete the Meaningful Auditory Integration Scale (MAIS); these assessments will be recorded and independently scored by research staff. Parents and children will complete four standardized Family Interaction Tasks (FIT) at baseline and annual assessments which will be videotaped and coded by two observers using (1) the DPICS coding system to provide an additional objective measure of parenting behaviors, and (2) the Systematic Analysis of Language transcripts (SALT) system for assessment of child language production. For families in the FCU-DHH condition, the FIT videos will also be used by parent coaches in feedback sessions. To increase retention during the study, we will also ask parent participants to complete a "Locator Information" form during baseline and annual assessments. The form lists alternative methods that parents agree can be used to locate them if their primary contact information changes or becomes disconnected during the study. During the initial informed consent process, the participant will indicate whether or not they choose to provide this information via an initialed checkbox on the consent document. If yes, either: a) the online survey will be programmed to display the Locator Form questions; b) the data collector will provide the Locator Information form in the mailed packet; or c) the data collector will ask for that information in a phone call. Any data received by mail will be entered into and stored in REDCap, which will be consulted to determine whether or not to provide copies of the Locator Information Form at follow-up assessments. Both the informed consent document and the text at the top of the locator form emphasize that completing the form is optional. If a research staff member uses this form to locate a participant by contacting a relative/friend listed by the participant, care will be taken to only indicate that we are trying to locate the individual in relation to a study. There will be no disclosure of the nature of the study, and therefore, no disclosure of the child's hearing loss.

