## Statistical Analysis Plan

All tests will be two-sided with a 5% significance level and will be conducted in SAS. Analysis methods will account for clustering within parent coaches (i.e., statistical correlation among the outcomes from participants who share the same interventionist). Therefore, analysis of our primary outcome (parenting behaviors as measured by PARYC score at the first 6-month follow-up) will be achieved with linear mixed-effects modeling, with random effects to account for this clustering. A fixed effect for trial arm (FCU-DHH vs. TAU) will be the primary covariate of interest. Additional analyses will address each outcome over time (i.e., PARYC scores, PARCHISY scores, measures of child behavior, parent report and objective adherence with HA/CI, and language development). In longitudinal analyses, linear mixed effects modeling will be adjusted to account for the additional level of correlation among outcomes from the same subject (e.g., a random time effect or an unstructured covariance). Fixed effects will include trial arm, time (categorical or continuous variable), and their interaction, with the interaction being of primary interest. Because rolling study enrollment is necessary, some parent–child dyads may have fewer observations than others. Recommended statistical approaches will be used for missing data within interventionists (e.g., multiple imputation at the subject and cluster level). Sensitivity analyses will be considered and dictated by the type of missing data. We will measure potentially important predictors (e.g., sex, race, parental age, socioeconomic status, degree of hearing loss, type of hearing rehabilitation device, and baseline language development) and statistically compare the balance of the two trial arms. Secondary analyses will include these variables as covariates. Stratified randomization (by device type and poverty level) will be accounted for in analyses.

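### The primary model omits baseline PARYC, and the inputs behind 125 dyads are not given: if a medium effect means 0.5 SD, power is 78% without clustering or loss and about 63–76% with assumed modest amounts of both

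*Combined protocol and SAP*

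**What the plan says.** **Sample size.** The Subject Children form (Section 2, item C) plans "72 dyads randomized to the intervention and 53 dyads randomized to the control condition". It continues: "This number was determined by our biostatistician based on the individually-randomized trial design", alpha .05, "the potential of clustering at the interventionist level, and the need to detect a medium-sized effect on the primary outcome", which it names as parenting behaviors. Neither the protocol nor the SAP gives a numeric effect size, a PARYC standard deviation, a target power, an ICC or an allowance for loss after randomization.

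**Primary analysis.** The SAP and the Aim 4 data analyses text of the protocol both specify a linear mixed model for PARYC at the first 6-month follow-up, with random effects for coaches. "A fixed effect for trial arm (FCU-DHH vs. TAU) will be the primary covariate of interest". The SAP adds that the stratification factors, device type and poverty level, will be accounted for. Other predictors enter secondary analyses only. The example list of these includes baseline language development but not baseline PARYC.

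**Baseline PARYC.** The Aim 4 description of parent measures puts "the 24-item PARYC (10 minutes") in the baseline and annual battery. Section 2, item C says that families were randomized once they had completed baseline. The score is therefore available before allocation for every randomized dyad, apart from item or form non-response.

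**The concern.** The size is presented as sufficient for a medium effect after coach clustering has been considered. On the common reading of medium as 0.5 SD, 72 against 53 falls just under 80% power before any clustering or loss is counted. Nothing is then left to absorb either. The 125 are counted at randomization, so the extra children allowed for in item C (families who consented but never completed baseline) do not cover loss between randomization and 6 months.

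The plan also leaves out of its primary model the covariate likely to be most informative, although it already holds it.

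What is at stake is how a null primary result is read. With the stated justification behind it, such a result could be taken to rule out a medium effect. On the assumptions shown below, the planned analysis would miss a true 0.5 SD difference about 24–37% of the time.

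**Working it through.** **Inputs from the documents.** Two-sided 5% test (SAP). 72 and 53 dyads (Subject Children form, Section 2, item C). 10 coaches (Aim 5 study population), which is 72/10 = 7.2 intervention dyads per coach. Coaches deliver only the intervention, so clustering applies to that arm alone.

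**Assumptions, none stated in the documents.** Effect d = 0.5 or 0.55 SD. ICC 0.01–0.05. Loss 5–20%, equal in both arms. Correlation r between baseline and 6-month PARYC of 0.3–0.6. 80% power serves only as a conventional benchmark.

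**The plan's own figure.** 125 cannot be reproduced, because the inputs needed are not given.

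**Formula.** V = DE/n₁ + 1/n₀, with DE = 1 + (m − 1) × ICC and m = n₁/10. Power is Φ(d/√V − 1.960) by the normal approximation (upper figures), or from the noncentral t (lower figures). With clustering, the t uses Satterthwaite df = V² / [(DE/n₁)²/9 + (1/n₀)²/(n₀ − 1)].

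**1. No clustering, no loss, 0.5 SD.** V = 1/72 + 1/53 = 0.03276, so SE = 0.181 and d/SE = 2.763. Power is 78.9% (normal) or 78.3% (t, 123 df). The effect detectable with 80% power is (1.960 + 0.842) × 0.181 = 0.507 SD.

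**2. ICC 0.05, no loss, 0.5 SD.** DE = 1 + 6.2 × 0.05 = 1.31. V = 1.31/72 + 1/53 = 0.03706 and SE = 0.1925. Power is 71.1% (df about 31) to 73.8%.

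**3. ICC 0.05, 15% loss, 0.5 SD.** n₁ = 61.2, n₀ = 45.05, m = 6.12, DE = 1.256, V = 0.04272, SE = 0.2067. Power is 65.0–67.7%.

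**4. Corners of the assumed range at 0.5 SD.**

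| ICC | Loss | Power |
|---|---|---|
| 0.01 | 5% | 73.5–75.8% |
| 0.01 | 20% | 66.2–68.7% |
| 0.05 | 5% | 69.2–71.9% |
| 0.05 | 20% | 62.6–65.4% |

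The range is about 63–76%.

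**5. A different reading of medium.** At 0.55 SD, power is 85.4–86.0% with no clustering or loss, 79.1–81.5% at ICC 0.05 with no loss, and 73.2–75.8% at ICC 0.05 with 15% loss.

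**6. Adding baseline PARYC.** Multiply V by (1 − r²), which takes the ICC as unchanged by adjustment. At 0.5 SD and ICC 0.05:

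| r | No loss | 15% loss |
|---|---|---|
| 0 (planned) | 71.1–73.8% | 65.0–67.7% |
| 0.3 | 75.1–77.7% | 69.1–71.8% |
| 0.5 | 82.8–85.1% | 77.3–79.8% |
| 0.6 | 88.2–90.1% | 83.4–85.6% |

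**The case against.** A reader might infer that the sample-size calculation is wrong, or that clustering was mentioned but never built in. The documents do not support this.

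- **The numbers fit a design inflated for clustering.** Two arms of 53 give 80.1% power at 0.55 SD (noncentral t, 104 df). The ratio 72/53 = 1.358 is the design effect that would bring the coached arm back to 53 effective dyads. With 7.2 dyads per coach this is ICC = 0.358/6.2, about 0.058. The reconstruction is an inference, as the documents do not state it. It shows that 72 + 53 is compatible with the stated rationale at about 0.55 SD with no loss. This stands, and it rules out calling the size an arithmetic error.
- **The derivation may be elsewhere.** A grant Research Strategy is listed among the attachments but is not part of the documents. This stands too.
- **Any single low figure is one scenario.** The 65–68% belongs to ICC 0.05 with 15% loss, and neither value is in the documents. Lighter assumptions give up to about 76%, so the range is what should be reported.
- **The model is not strictly unadjusted.** If device type and poverty level explained 5% of the variance (assumed), the figure with no clustering or loss would be 80.3%. With ICC 0.05 and 15% loss, the same 5% gives only 69.1% (t, without the Satterthwaite correction).
- **Repeated PARYC scores are already modelled.** This is true of the additional longitudinal analyses. It does not change the primary comparison.

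None of this explains why baseline PARYC is left out of the primary model.

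**Conclusion.** Two points hold. First, the primary model leaves out a baseline measurement of its own outcome, and including it would improve precision at no data-collection cost. Second, the justification for 125 dyads cannot be checked, because its effect size, power, ICC and loss allowance are not given.

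The power shortfall is conditional. If medium means 0.5 SD, power is 78% without clustering or loss and about 63–76% over the assumed ranges. If it means 0.55 SD, power is close to 80% at ICC 0.05 with no loss and about 73–76% with 15% loss. These figures rest on 10 coaches, clustering in the intervention arm only, equal loss by arm, and no gain from the stratification factors.

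The gain from baseline adjustment depends on a correlation that the documents do not give. At r = 0.5 it recovers most or all of the gap at 0.5 SD, but at r = 0.3 only part of it.

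**What to change.** **Main change.** Keep 125 dyads. In the SAP and in the protocol's Aim 4 data analyses, add baseline PARYC to the primary model alongside device type and poverty level. It can enter as a covariate, or as a response with a baseline mean common to both arms. The second form also keeps dyads that have a baseline but no 6-month score.

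Date the change and state that it was made before any unblinded analysis. This matters because recruitment was almost complete at the 2024 continuation review (two dyads remaining), and the documents do not say whether outcome data have been analysed. If they have been seen by arm, report the baseline-adjusted result as a labelled sensitivity analysis and keep the planned model as primary.

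**Secondary change.** In the justification of the number of children, state the sponsor's own effect size in SD units, PARYC SD, target power, ICC, number of coaches and loss allowance. The ICC and loss values used here are illustrations and should not be adopted as the design basis. If the planning effect was larger than 0.5 SD, saying so would prevent a null result from being read as excluding 0.5 SD.

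**Cost.** One covariate already collected, a dated SAP amendment and a few lines of text. No further enrolment or measurement is needed. The stated sensitivity may look less favourable than the present wording suggests.

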### SECTION 3. Wards of the State

If you need to activate this section:

- go to the Subject Demographics section;
- select "Wards of State (Children)" in the categories of subjects and controls to be included in your study;
- save that section.

#### A. 45 CFR 46.409(a)

Please indicate which category describes your research proposal:

- ☐ Research is related to subjects' status as ward of the state.
- ☐ Research is conducted in schools, hospitals, or similar setting(s) in which the majority of children involved in the study are NOT wards.

#### B. 45 CFR 46.409(b)

Federal regulations state that an advocate must be appointed in circumstances where investigators enroll wards of the state for research studies which are greater than minimal risk **specifically risk category 3 or 4**. Please answer the following questions:

a) Will the advocate serve in addition to a guardian or in loco parents?

- ☐ Yes ☐ No

b) Check the applicable item:

- ☐ Each child will have their own advocate.
- ☐ One advocate will serve for all children enrolled in the study.
- ☐ N/A

c) Explain why the advocate has the background and experience to serve as an advocate for the study.

d) Federal regulations state that an advocate cannot be associated with the study, investigator or organization. Please provide assurances that the advocate does not meet any of the criteria listed above.

### SECTION 4. Children Located Outside the State of Kentucky

Does your study involve children outside the state of Kentucky? ☒ Yes ☐ No

Provide information regarding the state definition of legally authorized representative, child, or guardian, as applicable to the research and to the federal definitions. [If the research is to be conducted in more than one state outside of Kentucky, provide this information for each state.]:

We have taken the most conservative definition of a legally authorized guardian for all states: biologic or adoptive custodial parent, or a court-appointed legal guardian. Even though some states may have other exceptions, for simplicity, we will ask the following question(s) for every participant during the consent process: "are you the biologic or adoptive custodial parent of this child?" If no, "are you a court-appointed legal guardian of this child?"

#### Guidance on Consent and/or Authorization by a Legally Authorized Representative

Consistent with Kentucky health care decision statutes for choosing a legally authorized representative for children, the following responsible parties in the order of priority listed shall be authorized to make research participation decisions on behalf of the child: (a) the judicially-appointed guardian of the person, if the guardian has been appointed and if the decisions to be made under the consent are within the scope of the guardianship; (b) the parent of the child.

#### Definitions

For definitions of "child/children", emancipated individuals, "legally authorized representative", "guardian", "assent", and "permission", see the [ORI/IRB Informed Consent Standard Operating Procedures \(SOP\)](#).

**INFORMED CONSENT/ASSENT PROCESS/WAIVER****0 unresolved  
comment(s)**

For creating your informed consent attachment(s), please download the most up-to-date version listed in "All Templates" under the APPLICATION LINKS menu on the left, and edit to match your research project.

Additional Resources:

- [Informed Consent/Assent Website](#)
- [Waiver of Consent vs. Waiver of Signatures](#)
- [Sample Repository/Registry/Bank Consent Template](#)

**Consent/Assent Tips:**

- If you have multiple consent documents, be sure to upload each individually (not all in a combined file).
- If another site is serving as the IRB for the project, attach the form as a "Reliance Consent Form" so the document will not receive a UK IRB approval stamp; the reviewing IRB will need to stamp the consent forms.
- Changes to consent documents (e.g., informed consent form, assent form, cover letter, etc...) should be reflected in a 'tracked changes' version and uploaded separately with the Document Type "Highlighted Changes".
- It is very important that only the documents you wish to have approved by the IRB are attached; DELETE OUTDATED FILES -- previously *approved* versions will still be available in Protocol History.
- Attachments that are assigned a Document Type to which an IRB approval stamp applies will be considered the version(s) to be used for enrolling subjects once IRB approval has been issued.

Document Types that do NOT get an IRB approval stamp are:

- "Highlighted Changes",
- "Phone Script", and
- "Reliance Consent Form",
- "Sponsor's Sample Consent Form".

**How to Get the Section Check Mark**

1. You must:
  - a) provide a response in the text box below describing how investigators will obtain consent/assent, and
  - b) check the box for at least one of the consent items and/or check mark one of the waivers
2. If applicable attach each corresponding document(s) **as a read-only PDF**.
3. If you no longer need a consent document approved (e.g., closed to enrollment), or, the consent document submitted does not need a stamp for enrolling subjects (e.g., umbrella study, or sub-study), only select "Stamped Consent Doc(s) Not Needed".
4. After making your selection(s) be sure to scroll to the bottom of this section and SAVE your work!

**Check All That Apply**

- ☒ Informed Consent Form (and/or Parental Permission Form and/or translated short form)  
☒ Assent Form  
☒ Cover Letter (for survey/questionnaire research)  
☒ Phone Script  
☒ Informed Consent/HIPAA Combined Form  
☐ Debriefing and/or Permission to Use Data Form  
☐ Reliance Consent Form  
☐ Sponsor's sample consent form for Dept. of Health and Human Services (DHHS)-approved protocol  
☐ Stamped Consent Doc(s) Not Needed

**Attachments**

Attach Type	File Name
Assent Form	Aim 4 child assent (6yr+)_CLEAN 3.16.23.pdf
Survey Consent	Aim 4_Student_BIT scoring consent.pdf
Informed Consent/Parental Permission	Aim4_Additional Caregivers_CLEAN_7.15.22.pdf
Informed Consent/Parental Permission	Aim 5_Parent interviews.pdf
Informed Consent/Parental Permission	Aim 5_Stakeholder interviews_CLEAN 9.18.25.pdf

**Informed Consent Process:**

Using active voice, in the text box below, describe how investigators will obtain consent/assent. Include:

- the circumstances under which consent will be sought and obtained
- the timing of the consent process (including any waiting period between providing information and obtaining consent)
- who will seek consent
- how you will minimize the possibility of coercion or undue influence
- the method used for documenting consent
- if applicable, who is authorized to provide permission or consent on behalf of the subject
- if applicable, specific instruments or techniques to assess and confirm potential subjects' understanding of the information

Will electronic consent form/process be utilized on-site or remotely for this study?

☒ Yes ☐ No

If yes, in addition to addressing the above bullet points, describe the e-consent method and platform, including any hyperlinks, videos, or enhancements used to convey information, if applicable. Attach a representation of the e-consent with signature fields. For guidance, see the ORI [E-Consent web page](#).

Note: all individuals authorized to obtain informed consent should be designated as such in the E-IRB "Study Personnel" section of this application.

Special considerations may include:

- Obtaining consent/assent for special populations such as children, prisoners, or people with impaired decisional capacity
- *Research Involving Emancipated Individuals*  
If you plan to enroll some or all prospective subjects as emancipated, consult with UK legal counsel **prior to submitting this application to the IRB**. Include research legal counsel's recommendations in the "Additional Information" section as a separate document.
- *Research Involving Non-English Speaking Subjects*  
For information on inclusion of non-English speaking subjects, or subjects from a foreign culture, see IRB Application Instructions for Recruiting Non-English Speaking Participants or Participants from a Foreign Culture.
- *Research Repositories*  
If the purpose of this submission is to establish a research repository describe the informed consent process. For guidance regarding consent issues, process approaches, and sample language see the [Sample Repository/Registry/Bank Consent Template](#).

Eligible participants in all study aims who are willing to enroll will each be individually informed in detail about the study goals and procedures, including: why they are being invited to participate; who is conducting the study; what is the study's purpose; exclusion criteria; study location and time requirements; what they will be asked to do; possible risks and discomforts; possible benefits; voluntariness of participation; costs of participation; confidentiality and its limits; rights to end participation early; payment for their time; and contact information for the PI and Office of Research Integrity at the University for questions, suggestions, concerns, or complaints. A copy of the signed informed consent form will be provided to each participant.

